12.8.2 Secondary Efficacy Analyses

Secondary efficacy analyses will be presented for ITT population.

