### 6.2. Secondary Endpoint(s)

Secondary endpoints for this study include:

- Subject retention in each group will be assessed by percentage of subjects who remain on the study at Week 6, and Week 8/EOS. Reasons for dropout will be documented.
- Time-on-task, averaged over all VR sessions, will be assessed at Week 6 and Week 8/EOS. Time on task will be automatically recorded by the VR system after each session.

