### Randomization

After Screening, subjects deemed eligible by the Investigator will be contacted by investigator site staff to be informed they are qualified to participate in the study. Randomization will occur after confirmation of eligibility and continued subject interest are verified. Subjects will be randomly allocated to either the treatment group (BVR-100) or the control (BES-100) group. Randomization will be assigned via an interactive web responses system (IWRS) in a 1:1 ratio to either BVR-100 or to BES-100. A VR headset pre-loaded with either BVR-100 or BES-100 will be shipped to the subject's address. Subjects will not be informed of their intervention allocation. In order to secure subjects blinding, subjects will have no prior experience with CBT. Subjects will be instructed not to share descriptions of the intervention they are receiving with investigator site staff during visits and discouraged from discussing details of the therapy outside the study. The Baseline visit will be scheduled to occur within 5-7 days of the randomization visit, to allow adequate time for VR device delivery/receipt. However, it could occur earlier if the device is received earlier. If, due to delays with device delivery/receipt, an extension beyond the 7 days is necessary, Medical Monitor approval will be required.

Upon confirmation of device delivery, a member of the unblinded site support team will contact the subject to confirm receipt of the device, to establish a relationship, and remind the subject that they would be the only contact for any device related issues throughout the duration of their participation in the study. After this is confirmed, the Baseline telehealth visit with the investigator site staff can take place.

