10.2 Full Analysis Set (FAS)

The Full Analysis Set (FAS) consists of all subjects enrolled and randomized into the study.

The FAS population will be used for summaries of subject disposition, demographic and baseline characteristics. Subjects will be analyzed according to the treatment group they were assigned at randomization.

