10.4 Intent-to-Treat (ITT) Population

The Intent-to-Treat (ITT) population consists of all randomized subjects who have at least one VR session.

The ITT population is the primary population to analyze efficacy endpoints. Demographic and baseline characteristics of the ITT population will also be presented. Subjects will be analyzed according to the treatment they received.

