11.17.2 Subject Retention Rate

Subject retention rate will be derived at Week 6 and Week 8/EOS for each of treatment groups.

Subject Retention Rate at Week 6 or Week 8/EOS =

$$\frac{\text{Number of subjects on the study at Week 6 or Week 8/EOS}}{\text{Total number of subjects in that treatment group}} * 100$$

Note: Subject who do not perform Week 6 but perform Week 8 will still be counted as subjects remaining on the study at Week 6.

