12.1 Subject Disposition

The number and percentage of subjects in screened, Enrolled Population, FAS population, Safety Population, Per-Protocol population and ITT population will be presented by treatment groups and total. Percentages for FAS population is based on Enrolled Population and percentages for all the other populations will be based on FAS population.

Number and percentage of subjects who completed the study, number and percentage of subjects who failed screening along with their reasons, number and percentage of subjects who terminated the study early along with their reasons will be summarized separately by treatment group and total. Reasons for screen failure will be displayed as in CRF. Percentages will be based on all screened subjects who signed ICF. Reason for discontinuation will be displayed in the descending order of "Total" column and percentages will be based on FAS population.

A flow diagram of subject disposition (CONSORT flow diagram) illustrating the progress of subjects throughout the study from screening to study completion/discontinuation will be provided.

Note that Enrolled Population and FAS population will be displayed by planned treatment and all other populations will be displayed by actual treatment.

Subject disposition information, status of inclusion exclusion criteria and subjects excluded from ITT analysis will be listed by subject who are screened.

Above analysis details are specified in DDP Table 14.1.1.1, Table 14.1.1.2, Figure 14.1.1.1, Listing 16.2.1.1, Listing 16.2.1.2 and Listing 16.2.3.1

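### Retention is calculated only among subjects who had a VR session, so losses between randomization and the first session are left out of the rate

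*SAP*

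**What the plan says.** Protocol 6.2 defines the secondary endpoint without any condition on device use: "Subject retention in each group will be assessed by percentage of subjects who remain on the study at Week 6, and Week 8/EOS". SAP 11.17.2 turns this into a ratio whose denominator is "Total number of subjects in that treatment group", and the formula names no analysis population.

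The population is fixed elsewhere. SAP 12.8.2 says "Secondary efficacy analyses will be presented for ITT population", and the Section 16 summary table also lists the retention rate under ITT. Despite its name, this is not an all-randomized set. SAP 10.4 reads: "The Intent-to-Treat (ITT) population consists of all randomized subjects who have at least one VR session".

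The SAP does have an all-randomized set (10.2): "The Full Analysis Set (FAS) consists of all subjects enrolled and randomized into the study". Its stated uses do not include retention: "The FAS population will be used for summaries of subject disposition, demographic and baseline characteristics".

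The first session comes some days after randomization. Protocol 7.1 says: "The Baseline visit will be scheduled to occur within 5-7 days of the randomization visit". The visit may be earlier if the headset arrives sooner, and later with Medical Monitor approval. The headset is shipped and the support team calls during that interval. The Baseline call, video onboarding and self-run set-up then precede the first session.

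**The concern.** A subject who withdraws or is lost during shipping, the support call, the Baseline call or headset set-up never enters the ITT set. The retention rate treats that subject as if never randomized, so it measures persistence among starters and not retention from randomization.

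This matters because of what the figure is for. Protocol 4.3 uses drop-out and retention as two names for one quantity. Protocol 4.3 and 7.3.1 say that the sample size should support a reliable evaluation of drop-out and that the pilot informs a later RCT. The 25% attrition allowance in Protocol 15.1 is applied to the number recruited. A starter-based rate cannot be compared directly with that allowance. If it were used to size a trial that counts losses from randomization, too few subjects would be planned.

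**Working it through.** **1. The plan's own figure.** Protocol 15.1 and SAP 4.2 give 15 per arm, 25% attrition and 20 recruited per arm. 15 / (1 − 0.25) = 20 per arm, 40 in total. The stated figure is reproduced, and the allowance is taken from recruited subjects, not from starters.

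**2. The two rates.** Let N be the subjects in an arm with at least one session (the ITT set), R those still on study, and k those randomized who left before any session.

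- Planned rate: R / N
- Rate among all randomized: R / (N + k)
- Difference: (R / N) × k / (N + k)

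The difference is zero when k = 0 and positive whenever k ≥ 1 and R > 0. It does not depend on why the k subjects left.

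**3. Illustration near the actual size.** SAP Section 13 reports 52 subjects with a session at the January 2024 data cutoff. It gives neither the split by arm nor the number randomized. Assumptions: an even split (N = 26), 5 later dropouts (R = 21), and k from 0 to 4 per arm.

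| k per arm | Planned rate, 21/26 | All randomized, 21/(26 + k) | Difference (points) |
|---|---|---|---|
| 0 | 80.8% | 21/26 = 80.8% | 0 |
| 1 | 80.8% | 21/27 = 77.8% | 3.0 |
| 2 | 80.8% | 21/28 = 75.0% | 5.8 |
| 3 | 80.8% | 21/29 = 72.4% | 8.4 |
| 4 | 80.8% | 21/30 = 70.0% | 10.8 |

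The planned rate is the same in every row, so it carries no information about losses before the first session.

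**4. Illustration at the planned size.** With 20 randomized per arm and 15 retained, retention among all randomized is 15/20 = 75.0%, which matches the 25% allowance. If k of the 5 losses come before the first session, the planned rate is 15/(20 − k): 78.9% for k = 1, 83.3% for k = 2 and 88.2% for k = 3.

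**5. Consequence for the next trial.** For an assumed 100 evaluable subjects per arm, retention of 75% requires 100/0.75, rounded up to 134 randomized per arm. Planning on the starter-based 83.3% (k = 2) gives 100 × 18/15 = 120.

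**The case against.** The strongest objection is that these losses are reported elsewhere. SAP 12.1 counts the FAS, Safety and ITT sets by arm, with the latter two as percentages of the FAS. It tabulates early terminations with reasons on the FAS, lists subjects excluded from ITT and adds a CONSORT diagram. A reader might infer that the plan hides early losses, and it does not. What remains is narrower: no Week 6 or Week 8 retention rate on the FAS is specified, and the endpoint table carries only the starter-based figure.

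Second, a rate among starters has a rationale. Protocol 4.3 wants the sham to give similar retention during the intervention, and Protocol 15.3.2 treats retention as an aspect of compliance. That supports keeping the starter-based rate, but not making it the only one.

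Third, a reader might suppose that ITT reached this endpoint by oversight. SAP Section 13, item 7, applies it explicitly to both primary and secondary endpoints. It also replaced a stricter protocol set that only 24 of the 52 subjects met because of missing CEQ data, so the change moved towards inclusion. However, the stated reason concerns CEQ data and does not address retention.

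Fourth, a reader might infer a bias between arms. The documents do not show one. Until onboarding, subjects hold headsets of identical appearance and have seen no content. Onboarding and the first session are meant to take place on the Baseline day.

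Finally, retention is descriptive here, so no test result depends on it.

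**Conclusion.** The point holds as a conditional one. The SAP computes retention on a set that requires a VR session, and no section computes it on all randomized subjects. Retention is overstated relative to all randomized subjects if anyone leaves before a first session, and is unaffected if nobody does.

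It would go too far to say that the trial's retention is in fact overstated, because the number randomized is not given and k is unknown. The 3 to 11 points in the illustration rest on an assumed even split of the 52, 21 retained per arm, and one to four pre-session losses per arm. Nothing in the documents shows that k reached any of these values.

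The effect is mainly on the level of retention. It deserves correction because that level is a secondary endpoint meant to inform the next trial.

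**What to change.** In SAP 11.17.2, 12.8.2.1 and the Section 16 table:

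- Report retention at Week 6 and Week 8 with the FAS as denominator, by assigned arm.
- Classify each subject by actual study status at that week, on study or discontinued. Absence of a VR session should not by itself count as not retained, because a randomized subject could remain on study without one.
- Keep the ITT-based rate as a second, labelled row, so that persistence among starters can still be compared between the device and the sham.
- Show by arm the number lost between randomization and the first session.
- Leave time-on-task on ITT, since it is defined only over completed sessions.

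No new data are needed. The cost is some SAP wording, one extra table row and possibly a slightly less favourable retention figure.

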12.8.2.1 Subject Retention Rate

Descriptive summary of subject retention rate will be summarized for Week 6 and Week 8 by treatment groups. The analysis details are specified in DDP Table 14.2.3.1.

12.8.2.2 Time-on-Task

Total number of active days, total number of sessions, overall average Time-on-Task (minutes) will be summarized by treatment groups. Weekly average Time-on-Task (minutes) will be presented by treatment group and week. Above analysis details are specified in DDP: Table 14.2.3.2, Listing 16.2.6.2.

12.9 Exploratory Analyses

12.9.1 Descriptive summaries

Descriptive summary of change from baseline results for total LSAS score and subscores, CGI-S score and PHQ-9 score, and the observed scores will be summarized by treatment groups and week based on ITT population. Observed scores for CGI-I score and PGI-I score will be summarized by treatment groups and week based on ITT population. Descriptive summary of the number of required sessions completed during the study will be summarized by treatment groups based on ITT population. All scores will be listed based on all Enrolled Population

For LSAS summary parameters to be summarized are: LSAS Total Score, Fear of performance situations, Avoidance of performance situations, Fear of social interaction, Avoidance of social interaction, Total fear and Total avoidance. Average of LSAS score will be plotted using line plot by treatment group and week. All listings are based on the Enrolled Population.

12.9.2 Inferential Summaries

The independent t-test or Mann-Whitney U test will be used to check the significant difference between treatment groups. Exact p-value obtained will be presented in summary tables. Normality test will be performed based on the methods as described in section 12.8.1.2.

Above analysis details are specified in DDP: Table 14.2.4.1, Table 14.2.4.2, Table 14.2.4.3, Table 14.2.5.1, Table 14.2.5.2, Figure 14.2.4.1.

Fisher's Exact Test for Independence of Responders

Since sample size of the responders is expected to be small, the association of responders between the treatment groups will be investigated using Fisher's exact test. Fisher's exact test will be used to compare the proportion of respondents between the treatment groups.

Descriptive statistics and p-values from the test will be provided.

Assumptions

- Variables are categorical.
- All observations are independent.

Reference SAS Program:

```
proc freq data = <INDATA>;
  tables <TESTVAR1>*<TESTVAR2> / fisher;
run;
```

Hypothesis:

H_0 : There is no association between treatment group and responders rate.

vs.

H_1 : There is association between treatment group and responders rate.

Above analysis details are specified in DDP Table 14.2.6.1, Listing 16.2.6.3.1, Listing 16.2.6.3.2, Listing 16.2.6.4, Listing 16.2.6.5, Listing 16.2.6.6, Listing 16.2.6.7

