***PART 1 (investigator site staff during telehealth Visit 3):***

- Clinician administers C-SSRS.
- Clinician administers LSAS.
- Clinician administers CGI-S.
- Collect any AEs.
- Review concomitant medication changes.
- Subject completes PHQ-9.
- Prior to ending the telehealth visit, remind the subject regarding Part 2 of the visit, which is completed independently at home by the subject, where they will be responsible for three activities:
  - Viewing the video for VR onboarding, a link for which will be sent immediately following the conclusion of Baseline, Part 1;
  - Completing the first VR session; and
  - Completing (electronically) the CEQ.

Remind the subject that throughout the duration of their study participation, they must not discuss anything regarding the intervention with the investigator site staff and that they could reach out to the designated unblinded site support team at any time.

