#### **15.4.2.4. Analysis of Exploratory Endpoints**

Likewise, descriptive statistics will be used to assess differences in the mean change from baseline in the LSAS, CGI-S and PHQ-9 at Weeks 2, 4, 6, and 8; differences in the mean change from CGI-S baseline score in the CGI-I and PGI-I at Weeks 2, 4, 6, and 8; and proportion of subjects with a "responder" status at the end of treatment at Week 8. Between-group differences in LSAS and responder status rates will be analyzed using Student's *t* tests and chi-squared tests, respectively.

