7.4 Exploratory Endpoints

- The overview of qualitative input obtained during Qualitative Interviews at Week 8.
- The mean change from baseline in LSAS scores at Week 2, Week 4, Week 6, and Week 8.
- The proportion of “responders”, that is, subject who are rated 1 (very much improvement) or 2 (much improvement) in the CGI-I at end-of-treatment (Week 8).
- The mean change from baseline in CGI-S score at Week 2, Week 4, Week 6, and Week 8.
- The mean PGI-I score at Week 2, Week 4, Week 6, and Week 8.
- The mean change from baseline in PHQ-9 score at Week 2, Week 4, Week 6, and Week 8.
- The number of VR sessions completed during the study.

8 Statistical Methods

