11.10 Baseline

Baseline is defined as the latest non-missing measurement prior to first video-guided VR onboarding session on week 1 day 1 including repeat assessments and unscheduled visits.

For CEQ scores, baseline is defined as first non-missing measurement taken after the first self-guided VR session and before week 1 day 7.

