12.8.1.2 Inferential Summaries

The independent t-test or Mann-Whitney U test will be used to check the significant difference between treatment groups. Exact p-value obtained will be presented in summary tables.

Normality test

Shapiro-Wilk test will be performed to test the normality of the two treatment groups and p-value will be interpreted. The test also assumes homogeneity of variances between the two treatment groups. Either one of the following tests will be performed:

- If Shapiro Wilk Test p-value > 0.05 then parametric T-Test will be used
- If Shapiro Wilk Test p-value < 0.05 then Mann-Whitney test will be used

Independent t-tests

Independent t-test will be used to compare mean scores (Observed and change from baseline scores) between treatment groups by visit.

Assumptions

- The samples are independent of one another.
- The sample is normally distributed within each of the two treatment groups.
- The variance should be homogeneous in the two treatment groups.

Reference SAS Program:

T-Test

```
proc ttest data = <INDATA>;
  class <TREATMENT>;
  var AVAL;
run;
```

Mann-Whitney test

```
proc npar1way data=<INDATA> wilcoxon;
  class <TREATMENT>;
  var AVAL;
run;
```

Hypothesis:

H_0 : Mean of parameter is the same in two treatment groups.

vs.

H_1 : Mean of parameter is not the same in two treatment groups.

Supportive analysis of the same will be presented for ITT and Per-Protocol population in a separate table.

Above analysis details are specified in DDP: Table 14.2.1.1, Table 14.2.1.2, Table 14.2.1.3, Table 14.2.1.4, Table 14.2.2.1, Table 14.2.2.2, Table 14.2.2.3, Table 14.2.2.4, Figure 14.2.2.5.

All CEQ scores will be listed in Listing 16.2.6.1

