Credibility / Expectancy Questionnaire (CEQ) scores	ITT Population	Primary: Descriptive summary, Independent t-test
	Per-Protocol Population	Supportive: Descriptive summary, Independent t-test
Secondary Endpoints		
Subject Retention Rate	ITT Population	Descriptive summary
Time-on-task		Descriptive summary
Exploratory Endpoints		
LSAS Overall & Subscores	ITT Population	Descriptive summary, Independent t-test
Responder Rate		Descriptive summary, Fisher's exact test
CGI-S Score		Descriptive summary
CGI-I Score		Descriptive summary
PGI-I Score		Descriptive summary
PHQ-9 Score		Descriptive summary
Safety Endpoints		
Adverse Events	Safety Population	Descriptive summaries on overall AE, relationship, severity etc.
C-SSRS		Descriptive summary

17 Change Log

Version	Author	Change Date	Description	Reviewer	Review Date
1.00	[REDACTED]	31-Jan-2024	First Approved Version	[REDACTED]	31-Jan-2024

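### The exploratory LSAS comparison is an unadjusted two-sample test on an unnamed variable; ANCOVA on the pre-exposure Baseline LSAS would settle the variable and generally be more precise

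*SAP*

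**What the plan says.** **Endpoint.** SAP 7.4 defines it as "The mean change from baseline in LSAS scores at Week 2, Week 4, Week 6, and Week 8". Protocol 6.3 does the same.

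**Summaries.** SAP 12.9.1 asks for both kinds of score: "Descriptive summary of change from baseline results for total LSAS score and subscores, CGI-S score and PHQ-9 score, and the observed scores".

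**Test.** SAP 12.9.2 states: "The independent t-test or Mann-Whitney U test will be used to check the significant difference between treatment groups". The choice between the two follows the Shapiro-Wilk rule of SAP 12.8.1.2. The Section 16 table lists only an independent t-test against "LSAS Overall & Subscores". Protocol 15.4.2.4 reads "Between-group differences in LSAS and responder status rates will be analyzed using" Student's t tests (for LSAS) and chi-squared tests (for responders). No section of either document contains an ANCOVA, a mixed model or any other baseline-adjusted comparison.

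**Baseline value.** Part 1 of the Baseline visit (Protocol 11.5.3) includes "Clinician administers LSAS", ahead of onboarding and the first VR session. SAP 11.10 states: "Baseline is defined as the latest non-missing measurement prior to first video-guided VR onboarding session on week 1 day 1". A Screening LSAS of at least 70 is also an entry criterion, so every eligible subject should have a pre-exposure value.

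**Allocation.** It is 1:1, with no stratification by LSAS stated (Protocol 7.2.1, SAP 4.3).

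**The concern.** There are two gaps. First, SAP 12.9.2 does not name the variable that is tested. The endpoint definition points to change, but the preceding section puts observed and change scores side by side, and nothing links the test to one of them. Second, whichever is meant, the test does not adjust for baseline. In a small trial without stratification on LSAS, a chance difference in Baseline LSAS passes into the estimate: upward with the imbalance for observed scores, and downward for change scores unless the outcome tracks baseline very closely.

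LSAS is exploratory here, but Protocol 4.3 and 7.3.1 use it for preliminary evidence of effectiveness, in line with the endpoints planned for the next RCT. The reader of this pilot will want one LSAS difference with an interval, and the variance figures that a baseline-adjusted RCT would need. The plan provides for neither.

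**Working it through.** **Sample size.** Protocol 15.1 takes 15 per arm from a cited rule and allows 25% attrition: 15 / (1 − 0.25) = 20 per arm, 40 in total. This reproduces the stated figure. SAP Section 13 reports 52 subjects in the ITT population, or 26 per arm if the split is even (an assumption).

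**Assumed inputs.** The documents give no LSAS SD and no baseline/Week 8 correlation. Let r be that correlation and k the Baseline SD divided by the Week 8 SD. Work in Week 8 SD units.

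**Variance per subject**
- Observed score: 1
- Change score: 1 + k² − 2rk
- ANCOVA: 1 − r²

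Change minus ANCOVA is (k − r)². It is never negative, and it is zero when r = k. With k = 1 the ratio of ANCOVA to change is (1 − r²) / [2(1 − r)] = (1 + r)/2.

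| k | r | Change variance | ANCOVA variance | ANCOVA / change | ANCOVA / observed |
|---|---|---|---|---|---|
| 1.0 | 0.3 | 1.40 | 0.91 | 65% | 91% |
| 1.0 | 0.5 | 1.00 | 0.75 | 75% | 75% |
| 1.0 | 0.7 | 0.60 | 0.51 | 85% | 51% |
| 0.8 | 0.5 | 0.84 | 0.75 | 89% | 75% |
| 0.8 | 0.7 | 0.52 | 0.51 | 98% | 51% |

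Estimating the slope multiplies the ANCOVA variance by about 1 + 1/48 = 1.02 at 26 per arm. That cancels the 2% gain in the last row.

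**Standard errors at 26 per arm, k = 1, r = 0.3 / 0.5 / 0.7.** The observed-score SE is √(2/26) = 0.277 throughout. Change: 0.328 / 0.277 / 0.215. ANCOVA, with the slope penalty: 0.267 / 0.243 / 0.200. Which unadjusted test is worse depends on the unknown r; with k = 1, ANCOVA has the smallest SE at all three values.

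**Chance imbalance.** The baseline difference between arms has SD √(2/n) in Baseline SD units.
- n = 26: 0.277. P(|difference| > 0.3) = 2[1 − Φ(0.3/0.277)] = 28%.
- n = 20: 0.316. P(|difference| > 0.3) = 2[1 − Φ(0.3/0.316)] = 34%.

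With k = 1, an imbalance D moves the observed-score difference by rD and the change-score difference by −(1 − r)D. At r = 0.5 and D = 0.3 these are +0.15 and −0.15 SD. ANCOVA removes both.

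**Simulation with the entry rule.** Assumptions: Screening LSAS at least 70, population mean 85, SD 20, Screening/Baseline correlation 0.8, true difference −10 points, 26 per arm, 8,000 replicates. At an enrolled correlation of 0.50 the SEs were 5.04 (observed), 4.85 (change) and 4.41 (ANCOVA) LSAS points. So ANCOVA variance was (4.41/4.85)² = 83% of change and (4.41/5.04)² = 77% of observed. Mean estimates were −10.02, −10.04 and −10.03: all three are unbiased over repeated randomisation. The estimate's correlation with baseline imbalance was 0.50, −0.44 and 0.01 respectively.

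**The case against.** The strongest reply is that baseline is already used. The endpoint is change from baseline, Protocol 15.4.2.4 names change before it names the t-test, and subtraction captures much of what a covariate would. This stands: the relevant comparison is change score against ANCOVA, where the saving is moderate and can be nil. The larger savings apply only if observed scores are tested.

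Four stronger readings are tempting, and the documents do not support them.

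- **LSAS is tested both ways.** The sentence "Independent t-test will be used to compare mean scores (Observed and change from baseline scores) between treatment groups by visit" is in SAP 12.8.1.2, which concerns the CEQ. SAP 12.9.2 refers to that section only for the normality test. The defect is an unnamed variable, not two declared tests.
- **Imbalance contaminates the SD passed to the next RCT.** A within-arm SD does not carry a between-arm difference. Which SD the RCT needs depends on its own model, which the documents do not give; a change-score RCT would properly use the change SD. SAP Section 13 also removes the future-trial SD rationale from the sample-size text.
- **The comparison is biased.** The error is a chance one, and all three estimators are unbiased over randomisation.
- **A material imbalance is to be expected.** A probability of 28% to 34% is appreciable, but below one half.

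It is also fair to say that LSAS is exploratory, that Protocol 15.4.2 disclaims formal hypothesis testing, and that SAP 12.3 tabulates Baseline LSAS by arm, so an imbalance would be visible. These points limit the stakes. But seeing an imbalance does not correct for it, and an exploratory estimate should still be the best that the collected data allow.

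**Conclusion.** The point holds as a modest, nearly free improvement to an exploratory analysis. SAP 12.9.2 should name the LSAS variable, and the comparison should adjust for the Baseline LSAS already collected.

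With equal SDs and a correlation of 0.3 to 0.7, the variance saving over a change-score test is 35% down to 15%, and over an observed-score test 9% up to 49%. If the Baseline SD is smaller than the Week 8 SD, which the entry threshold could cause, the saving over change scores can shrink to nothing. The figures rest on assumed correlations and SD ratios, an even split of 52 subjects and complete Week 8 data. Missing values are not imputed (SAP 9.1.1), so the number analysed may be lower and chance imbalance correspondingly larger.

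The finding does not undermine the primary CEQ analysis or the secondary endpoints.

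**What to change.** In SAP 12.9.2 and the Section 16 table:

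- Make the LSAS comparison an ANCOVA of change from baseline in LSAS total score at Week 8, with treatment and Baseline LSAS (SAP 11.10) as the terms. With baseline in the model, change and observed scores give the same treatment difference, so the question of which to test disappears.
- Fit the same model at Weeks 2, 4 and 6, and for the subscores, as secondary results.
- Report the adjusted difference, its 95% CI, the residual SD and the baseline/Week 8 correlation. With the raw SDs these let the RCT be sized under either an adjusted or a change-score analysis.
- Keep the observed and change summaries of SAP 12.9.1 descriptive.
- Keep the Mann-Whitney test on change only as a sensitivity analysis, for clearly non-normal residuals.

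The analysis stays exploratory. The cost is SAP wording, a few lines of SAS and one degree of freedom; no new data are needed.
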